More than 650 patients have received Denileukin diftitox in clinical studies for a variety of diseases including CTCL, B- and T-cell NHL, Hodgkin's disease, CLL, acute graft versus host disease, rheumatoid arthritis, HIV infection, recent-onset insulin dependent diabetes mellitus or psoriasis. Overall, at doses ranging from 0.5 to 31 µg/kg/d, the most common adverse events were fever, nausea/vomiting and other flu-like symptoms; acute hypersensitivity reactions including hypotension, dyspnea, rash, and back pain; a vascular leak syndrome; delayed-onset rash; elevated hepatic transaminases; and hypoalbuminemia. The dose-limiting toxicity for lymphoma patients was defined at the 27 µg/kg/d dose level by persistent, moderate-to-severe nausea, vomiting, fever, chills, and/or asthenia. While the same events were reported at lower dose levels, the severity of the events was greater at doses above 19 µg/kg/d for 5 consecutive days. Although not statistically significant, it appeared that adverse events might be dose-related. In the largest clinical study to date, the Phase III pivotal trial, no patients discontinued the study secondary to lymphopenia, and myelosuppression was uncommon and did not limit treatment. Denileukin diftitox, produced by Eisai Pharmaceuticals, is commercially available and approved by the FDA for administration at 9 or 18mcg/kg/day in patients with lymphomas expressing CD25.

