## **2 ELIGIBILITY ASSESSMENT AND ENROLLMENT**

### **Eligibility Criteria:**

#### **2.1 Inclusion Criteria**

- 2.1.1 Patients must have serum antibodies directed to HTLV-I.
- 2.1.2 All patients must have a histologically confirmed diagnosis of adult T-cell leukemia/lymphoma and more than 10% of the malignant cells must express CD25.
- 2.1.3 All stages of Tac-expressing adult T cell leukemia except smoldering are eligible: patients with chronic, lymphomatous or acute ATL are eligible. (See appendix 2 for characteristics of patients with the various stages of ATL)
- 2.1.4 Patients must have measurable disease. All patients with greater than 10% abnormal (i.e. TAC homogenous strongly expressing) PBMC in the peripheral blood will be deemed to have measurable disease.
- 2.1.5 The patient must have a granulocyte count of at least  $1000/\text{mm}^3$  and a platelet count of greater than or equal to  $50,000/\text{mm}^3$ .
- 2.1.6 Patients must have a creatinine of less than 2.0 mg/dl.
- 2.1.7 Omission of cytotoxic chemotherapy for ATL for 3 weeks prior to entry into the trial is required. However, patients receiving corticosteroids will be eligible.
- 2.1.8 Patients must have a life expectancy of greater than 2 months.
- 2.1.9 Eligible patients must be  $\geq 18$  years old. There is no upper age limit.

- 2.1.10 Patients must have SGOT and SGPT value  $\leq 2.5$  times the upper limit of normal and bilirubin  $\leq 3.0$ /dl. If a liver function test is judged to be elevated due to the underlying ATL, this parameter will be considered an unevaluable parameter for toxicity determinations.
- 2.1.11 Patients must have a serum albumin  $\geq 2.5$  g/dl
- 2.1.12 Patients must be able to understand and sign an Informed Consent form.
- 2.1.13 All patients must use adequate contraception during participation in this trial and for three months after completing therapy.

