### **3.2 Drug Administration**

Denileukin diftitox is for intravenous (IV) use only. Treatment of patients may be administered either on an inpatient or outpatient basis. Patients receiving denileukin diftitox at either 9 or 18 mcg/kg/day for 5 days will receive their first cycle as an inpatient, but if toxicities are acceptable, subsequent dosing may be administered as an outpatient. The daily dose is to be infused over 60 minutes.

Patient's baseline weight will be used to determine all doses of Denileukin diftitox®. Dosing will be adjusted if there is a  $\pm$  10% change in weight.

Patients will be premedicated with acetaminophen (650 mg po) and diphenhydramine (25-50 mg po), 30-90 minutes prior to each infusion and PRN for symptoms. Meperidine (25-50 mg IV) may be given if chills or rigors develop.

Patients will be monitored with vital signs (temperature, pulse, respiration and blood pressure) before and every 15 minutes during the Denileukin diftitox infusion, and then every 30 minutes for a total of 2 hours after the infusion.

Some patients may develop tumor lysis syndrome. If the patient is considered at risk for tumor lysis syndrome; allopurinol, hydration and alkalinsiation will be administered according to the discretion of the Principal Investigator.

The most common side effects observed are elevated transaminases, hypoalbuminemia, vascular leak syndrome, fatigue and flu-like symptoms. These side effects tend to occur less frequently with further cycles.

If infusional adverse reactions occur, the infusion should be discontinued or the rate should be reduced depending on the severity of the reaction (see Section 4.1). Denileukin diftitox dose may be modified at the discretion of the principal investigator. If the patient is unable to tolerate the 9mcg/kg/day dose it may be reduced to 4.5mcg/kg/day. If the patient is unable to tolerate the 18 mcg/kg/day dose it may be reduced to 9 mcg/kg/d. Allergic reactions to dose administration are possible, therefore appropriate drugs and medical equipment to treat acute anaphylactic reactions must be immediately available and study personnel must be trained to recognize and treat anaphylaxis. If symptom of moderate (grade 2) or severe (grade 3) hypersensitivity persist for longer than 6 hours despite treatment of symptoms, further treatment with Denileukin diftitox should be discontinued. If anaphylaxis occurs at any time, further treatment with Denileukin diftitox must be discontinued.

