#### 5.4.4 Safety Endpoint

Drug safety will be assessed by examining adverse events, laboratory abnormalities, physical examination and ECOG performance status change from baseline. Adverse events, serious adverse events and abnormal lab values will be graded according NCI CTC criteria. Their occurrence within 30 days from the last study treatment will be summarized for all patients. We will monitor after the 9th, 18th, 27th, and 36th patient. We will stop for toxicity if more than 5 patients experience grade 4 or greater toxicity attributed as possibly, probably or definitely related to Denileukin diftitox after the 9th patient, more than 10 patients experience toxicity after the 18th patient, more than 15 patients experience toxicity after the 27th patient, and more than 20 patients after the 36th patient. For monitoring, toxicity will be defined over the 28 day period after treatment begins. If the probability of toxicity is 1/3, we will have a 5% chance of stopping the trial early based on the toxicity stopping rule. If the probability of toxicity is 0.60, we will have a 73.2% chance of stopping the trial early. If the probability of toxicity is 0.70, we will have a 94.7% chance of stopping early. If at any time during the conduct of the trial two patients die due to toxicity attributed to Denileukin diftitox accrual to the study will be placed on hold and modifications discussed with the sponsor before reopening the study.

- 5.4.5 We anticipate enrolling 10-12 patients per year into the Denileukin diftitox trial. Thus, if the trial goes to completion (2nd stage) at the 9 mcg/kg/d dose we anticipate enrolling the 29 patients in approximately 2.5 years. If the trial proceeds to completion through the 18 mcg/kg/d dose, a total of 38 patients will be enrolled in approximately 3.5 years.

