## 9 SAFETY REPORTING REQUIREMENTS

### 9.1 Definitions

#### 9.1.1 Adverse Event

An adverse event is defined as any reaction, side effect, or untoward event that occurs during the course of the clinical trial associated with the use of a drug in humans, whether or not the event is considered related to the treatment or clinically significant. For this study, AEs will include events reported by the patient, as well as clinically significant abnormal findings on physical examination or laboratory evaluation. A new illness, symptom, sign or clinically significant laboratory abnormality or worsening of a pre-existing condition or abnormality is considered an AE. All AEs must be recorded on the AE case report form.

All AEs, including clinically significant abnormal findings on laboratory evaluations, regardless of severity, will be followed until satisfactory resolution. AEs should be reported up to 30 days following the last dose of study drug. AEs that are considered treatment related, expected, continuing, but not resolvable by 30 days after treatment completion (e.g., alopecia) will not be followed after the 30-day period.

An abnormal laboratory value will be considered an AE if the laboratory abnormality is characterized by any of the following:

- Results in discontinuation from the study
- Is associated with clinical signs or symptoms
- Requires treatment or any other therapeutic intervention
- Is associated with death or another serious adverse event, including hospitalization.
- Is judged by the Investigator to be of significant clinical impact
- If any abnormal laboratory result is considered clinically significant, the investigator will provide details about the action taken with respect to the test drug and about the patient's outcome.

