**Infusion-associated Reactions:** There are two distinct clinical syndromes associated with denileukin diftitox infusion, an acute hypersensitivity-type symptom complex and a flu-like symptom complex. Overall, 69% of patients had infusion-related, hypersensitivity-type symptoms. A flu-like syndrome was experienced by 91% of patients within several hours to days after denileukin diftitox infusion. The symptom complex consists of one or more of the following: fever and/or chills (81%), asthenia (66%), digestive (64%), myalgias (18%) and arthralgias (8%). In the majority of patients, three symptoms were mild to moderate and responded to treatment with antipyretics and/or anti-emetics. Antipyretics and/or anti-emetics were used to relieve flu-like symptoms; however, the usefulness of these agents in ameliorating these toxicities or as prophylactic agents to decrease the incidence of the acute, flu like toxicities has not been prospectively studied.

**Gastrointestinal** - The onset of diarrhea may be delayed and the duration can be prolonged. Dehydration, usually concurrent with vomiting or anorexia, occurred in 9% of the patients. The majority of transient hepatic transaminase elevations occurred during the first course of denileukin diftitox and were self-limited resolving within two weeks.

**Rash** - A variety of rashes were reported, including generalized maculopapular, petechial, vesicular bullous, urticarial and/or eczematous with both acute and delayed onset.

**Cardiovascular System** - Two patients, both of whom had known or suspected pre-existing coronary artery disease, sustained acute myocardial infarctions while on study. Ten additional patients (7%) experienced thrombotic events. Two patients with progressive disease and multiple medical problems experienced deep vein thrombosis. Another patient sustained a deep vein thrombosis and pulmonary embolus during hospitalization for management of congestive heart failure and vascular leak syndrome. One patient with a history of severe peripheral vascular disease sustained an arterial thrombosis. Six patients experienced less severe superficial thrombophlebitis. Thrombotic events were also observed in preclinical animal studies.

**Eyes:-** Loss of visual acuity usually with loss of color vision with or without retinal pigment mottling has been reported following drug administration. Recovery was reported in some of the affected patients; however most patients reported persistent visual impairment.

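### Section 2.1.10 lets a later drug-related grade 4 rise in a liver test attributed to ATL drop out of the toxicity stopping count

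*Combined protocol and SAP*

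**What the plan says.** Section 2.1.10 caps SGOT and SGPT at 2.5 times the upper limit of normal and bilirubin at 3.0, with no waiver for disease-related elevation. It then says of a liver test judged raised because of ATL that "this parameter will be considered an unevaluable parameter for toxicity determinations". It names no assessor, grade limit or time point.

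Four other places bear on this:

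- **5.4.4, stopping rule:** "We will stop for toxicity if more than 5 patients experience grade 4 or greater toxicity attributed as possibly, probably or definitely related to Denileukin". This boundary applies at the look at nine patients; the later boundaries are more than 10 of 18, 15 of 27 and 20 of 36. Toxicity is taken over the 28 days from the start of treatment. The rule does not mention 2.1.10.
- **5.4.4, safety summary:** adverse events, serious adverse events and abnormal laboratory values are graded and summarised for all patients, with no liver exception.
- **9.1.1:** "worsening of a pre-existing condition or abnormality is considered an AE".
- **9.2.2:** related grade 3 and 4 events go to the IRB at continuing review.

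**The concern.** What 2.1.10 sets aside is the parameter, not the baseline value. A patient whose AST is mildly raised by ATL at entry therefore has no evaluable AST for toxicity afterwards, whatever it does on treatment. Someone applying 2.1.10 would leave a drug-related grade 4 AST rise out of the stopping count; someone applying 5.4.4 alone would count it. The plan does not say which section governs.

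The liver is a poor place for this ambiguity. Section 3.2 says: "The most common side effects observed are elevated transaminases, hypoalbuminemia, vascular leak syndrome, fatigue and flu-like symptoms". On timing, 10.1.6 says: "The majority of transient hepatic transaminase elevations occurred during the first course of denileukin diftitox and were self-limited resolving within two weeks". Such rises fall inside the 28-day window. The study has moved to 18 mcg/kg/d, and 1.2.6 says that adverse events might be dose-related, although this was not statistically significant.

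At stake is a one-sided undercount in the only numerical toxicity stopping rule apart from the two-death hold.

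**Working it through.** **1. Does any other text restore the parameter?** No. Sections 9.1.1 and 9.2.2 and the safety summary in 5.4.4 keep the event on record. None of them says that it enters the stopping count.

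**2. What has been seen so far.** Appendix 5, nine patients at 9 mcg/kg/d, grades 1, 2, 3, 4:

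- AST 3+0+1+0 = 4
- bilirubin 2+0+1+0 = 3
- ALT 1+1+0+0 = 2
- alkaline phosphatase 2+0+0+0 = 2

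Liver abnormalities are common, but none is grade 4 and two entries are grade 3. The only grade 4 entry in the table is one neutropenia.

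**3. The plan's own stopping figures.** Let X be the cumulative number of patients with toxicity. For three looks, P(stop) = 1 − P(X₉ ≤ 5, X₁₈ ≤ 10, X₂₇ ≤ 15), computed by exact binomial recursion.

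| True probability | Stated in 5.4.4 | Looks at 9, 18, 27 | All four looks |
|---|---|---|---|
| 1/3 | 5% | 5.0% | 5.0% |
| 0.60 | 73.2% | 73.5% | 79.0% |
| 0.70 | 94.7% | 95.1% | 97.6% |

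The stated figures fit the first three looks. That is a separate matter, so both versions are shown below.

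**4. Effect of missed events.** Let f be the share of patients with toxicity whose only grade 4 event is in an excluded liver test. The documents do not give f; it is an assumption. The rule then sees p′ = p(1 − f). For example, 0.60 × 0.95 = 0.57 and 0.70 × 0.95 = 0.665.

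| f | p = 0.60, three looks | p = 0.70, three looks | p = 0.60, four looks | p = 0.70, four looks |
|---|---|---|---|---|
| 0 | 73.5% | 95.1% | 79.0% | 97.6% |
| 2% | 69.6% | 93.4% | 75.0% | 96.4% |
| 5% | 63.5% | 90.0% | 68.6% | 93.9% |
| 10% | 52.8% | 82.2% | 57.1% | 87.2% |
| 20% | 32.4% | 59.9% | 34.5% | 64.9% |

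To see what f requires, write f = q × h. Here q is the share of patients with an ATL-attributed liver test, and h is the share of toxic patients among them for whom that test is the only grade 4 event. An f of 5% needs, for instance, q = 20% and h = 25%. With no grade 4 liver event in nine patients, h may well be much lower.

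**5. One patient at a nine-patient look.** A single omission reverses the decision when exactly 6 of 9 have toxicity: C(9,6)p⁶(1 − p)³ = 25.1% at p = 0.60 and 3.4% at p = 1/3. For the 9 mcg/kg/d cohort that look is past. The figure would matter again only if counting restarted at 18 mcg/kg/d, which the plan does not say.

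**The case against.** **The event is still captured.** A reader might infer that these liver events vanish from the safety data. The documents do not support that: 9.1.1, the safety summary in 5.4.4 and 9.2.2 have no liver exception. Nor is there a flat contradiction with 9.1.1. An adverse event there need not be drug-related, so an event can be recorded and still be kept out of a drug-toxicity determination. This stands, and it confines the point to the stopping count.

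**The sentence may work elevation by elevation.** It gives no time point. It could mean only that an elevation judged due to ATL is not a toxicity, so that a post-dose rise judged drug-related is outside it. That is possible, but less natural: the word used is parameter, and the sentence sits in an entry criterion. That the judgement is made at entry is itself inferred from this position.

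**The effect on stopping is remote.** A missed patient matters only near a boundary and only without another related grade 4 event. If the true rate were 1/9 (one grade 4 entry among nine patients, used as an assumption), the chance of six or more of nine is about 0.01%. If counts run on across doses, as a look after the 36th of 38 patients suggests, the first nine contribute at most the one grade 4 entry in Appendix 5. The look at 18 could then reach at most 1 + 9 = 10, which does not exceed 10. The look at 27 would need 16 − 1 = 15 of the next 18. This stands as an argument about size. It does not make the rule clear.

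**Conclusion.** The point holds in a limited form. Followed literally, 2.1.10 removes a later drug-related grade 4 rise in an ATL-attributed liver test from the 5.4.4 stopping count, and nothing else in the plan puts it back. The direction is certain, since the count can only fall.

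The size is unknown and probably small. The number of affected patients is not given, no grade 4 liver event occurred at 9 mcg/kg/d, and the losses in the working require toxicity of 60 to 70% together with an assumed f. The experience at 18 mcg/kg/d is not in the documents.

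A reader might also infer that the 9 mcg/kg/d results understate liver toxicity. That is not shown: Appendix 5 reports liver tests and does not say whether any were set aside.

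**What to change.** Reconcile 2.1.10 with 5.4.4 and 9.1.1 by replacing the unevaluable rule with assessment against baseline. Suggested wording: *A liver test value at baseline that is judged due to ATL is not itself a toxicity. Any later worsening of CTC grade above the patient's own baseline is recorded as an adverse event. It counts in the 5.4.4 stopping rule if it is grade 4 or greater and at least possibly related to the drug.* State also who makes the attribution.

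The cost is a few sentences and no new sampling, since chemistry is already drawn daily in cycle 1 (3.4.1). Some disease-driven rises will be recorded and need attribution, including low-grade ones that the laboratory criteria in 9.1.1 might not have captured. The relatedness condition in 5.4.4 still filters these from the stopping count.

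The change concerns event counting only. Section 3.3 also rests on toxicity grades when it defines dose-limiting toxicity; how 2.1.10 applies there should be reconciled by the sponsor, and no clinical rule is proposed here.

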### 3.3 Treatment Modifications

Dose limiting toxicities are defined as toxicities attributed to study drug administration requiring discontinuation of drug. These consist of:

- Any episode of life threatening Denileukin Diftitox hypersensitivity.
- Any grade III or IV toxicity not easily reversible to grade 1 by standard supportive measures.

In those cases where a toxicity occurs, which is deemed related to the study drug by the Principal Investigator, additional dosing may occur once the toxicity has resolved by 2 grades or to grade 1. The daily dose may be reduced to 4.5mcg/kg/day, for patients in the 9 mcg/kg/d group, or to 9 mcg/kg/d for patients in the 18 mcg/kg/d group.

Patients with life threatening hypersensitivity reactions or grade III or IV toxicity that does not resolve to grade 1, will be taken off treatment but remain on study for follow-up evaluation.

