### **3.11 Off Study Criteria**

- 3.11.1 Patient noncompliance or request to withdrawal from the study  
3.11.2 Tumor progression and initiation of another treatment.  

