3.11.3 Completion of the protocol follow up period  
3.11.4 Death

### **3.12 Post-Treatment Evaluation (Follow-up)**

- 3.12.1 After completion or discontinuation of the study treatment, the patients will be serially followed monthly for the first three months and then at three month intervals unless the patient begins treatment for their ATL under the care of another physician.

At these interval visits, the patients will undergo the following evaluations which are described in Section 2:

- history and physical examination
- hematologic, serum studies
- sIL-2R $\alpha$
- Urinalysis
- tumor assessment
- flow cytometry

3.12.2 If clinically indicated patients shall undergo the following studies which are described in Section 2:

- skin biopsy
- skin testing.

3.12.3 Patients shall undergo apheresis on completion of therapy and the sample processed by Lab of Cellular Oncology for DNA microarray

3.12.4 After the first year the patients shall be followed every four months for the second year, every six months for the third through fifth year after completion of treatment, and then on a yearly basis.

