**Infrequent Serious Adverse Events** - The following serious adverse events occurred at an incidence of less than 5%: pancreatitis, acute renal insufficiency, microscopic hematuria, hyperthyroidism and hypothyroidism. Occasional patients experienced tumor lysis syndrome; patients at risk should receive appropriate prophylaxis prior to administration.

**Pregnancy:** Animal reproduction studies have not been conducted with denileukin diftitox. It is also not known whether denileukin diftitox can cause fetal harm when administered to a pregnant woman or affect reproductive capacity.

**Nursing Mothers:** It is not known whether this drug is excreted in human milk. Because many drugs are excreted in human milk, and because of the potential for serious adverse reactions in nursing infants, patients receiving denileukin diftitox should discontinue nursing.

**Cautions:** Women of child-bearing age and fertile men should be advised to use adequate and effective contraception during treatment with Denileukin diftitox and for at least six months after therapy. The effects of Denileukin diftitox on embryogenesis, reproduction, and spermatogenesis are unknown.

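### Criterion 2.1.13 requires three months of contraception after therapy, while the protocol's own Cautions in 10.1.6 advise at least six

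*Combined protocol and SAP*

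**What the plan says.** Two places in the combined protocol and SAP set a contraception period.

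- **Section 2.1, criterion 2.1.13**, is mandatory and written for everyone: "All patients must use adequate contraception during participation in this trial and for three months after completing therapy".
- **Section 10.1.6, Cautions**, is advice to fertile patients of either sex. They are to be told to use "contraception during treatment with Denileukin diftitox and for at least six months after therapy". The reason follows at once: "The effects of Denileukin diftitox on embryogenesis, reproduction, and spermatogenesis are unknown".

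Whether participation lasts beyond treatment matters, and several sections bear on it.

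- Section 3.3 says that patients stopped for certain toxicities "will be taken off treatment but remain on study for follow-up evaluation".
- Section 3.11.3 lists as an off-study event: "Completion of the protocol follow up period".
- Two other off-study events can occur at any time: "Patient noncompliance or request to withdrawal from the study" (3.11.1) and "Tumor progression and initiation of another treatment" (3.11.2).
- Section 3.12.1 has visits monthly for three months, then "at three month intervals unless the patient begins treatment for their ATL under the care of another physician". Section 3.12.4 carries follow-up on for years.

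**The concern.** A patient can meet 2.1.13 exactly and stop contraception at month three, while the protocol's own advice is to continue to month six or beyond. A mandatory rule should not be shorter than the minimum that the same document advises. Staff who work from the eligibility criteria would find three months there, and would meet six only in the adverse-event text.

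The protocol treats the reproductive risk as unresolved. Section 10.1.6 reports no animal reproduction studies, and 2.2.2 excludes pregnant women because fetal effects are not known. The only pregnancy test found in the text available is at eligibility (2.3.8). Appendix 1 lists none during cycles, and the Appendix 2 table is not in the text. Contraception is thus the main safeguard after entry, and its length should be stated once and consistently.

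Early exit is foreseeable. Section 3.10.1 stops treatment for progression after the first two cycles, and 1.2.8 reports no objective response in the nine patients given 9 mcg/kg/d. Progression followed by another therapy within six months of the last dose is a plausible route off study.

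**Working it through.** The plan has no computed figure to reproduce. The check compares two stated periods.

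**Inputs**

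- Mandatory period after therapy: 3 months (2.1.13), or longer while the patient is still participating.
- Advised minimum after therapy: 6 months (10.1.6, Cautions).
- m = months from last dose to going off study (3.11). Assumption: both periods are counted from the last dose.

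**Reading A: participation includes follow-up.** Sections 3.3 and 3.11.3 favour this reading, since both treat patients as on study after treatment ends.

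Binding period = max(3, m). Shortfall = max(0, 6 − max(3, m)).

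| Off study at month m | Binding period (months) | Shortfall against 6 (months) |
|---|---|---|
| 0 to 3 | 3 | 6 − 3 = 3 (3/6 = 50%) |
| 4 | 4 | 6 − 4 = 2 |
| 5 | 5 | 6 − 5 = 1 |
| 6 or later | 6 or more | 0 |

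**Reading B: participation means treatment only.** The binding period is 3 months whatever m is, so the shortfall is 6 − 3 = 3 months for every fertile patient. The protocol does not define participation, so this reading cannot be excluded.

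**Who falls in the gap under reading A.** These are patients who leave before month six by 3.11.1 or 3.11.2. Under 3.12.1, visits also end when ATL treatment starts under another physician. The text does not say whether that alone, without progression, takes the patient off study.

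**Does the drug's clearance favour six months over three?** Section 1.2.5 gives a terminal half-life of about 70 to 80 minutes and no accumulation between the first and fifth doses. Taking three months as 90 days:

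- 90 × 1,440 min = 129,600 min
- 129,600 / 80 = 1,620 half-lives
- 129,600 / 70 ≈ 1,851 half-lives

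Clearance gives no reason to prefer six months. The case for six is only that the protocol itself states it as the minimum.

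**After the change.** With 6 in place of 3, the binding period is max(6, m) under reading A and 6 under reading B. The shortfall is 0 under both.

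**The case against.** The strongest reply is that the two texts can both be obeyed. One is an entry rule with a floor of three months. The other tells staff to advise at least six, and that advice is not limited to patients still on study. If staff follow 10.1.6, every fertile patient hears six months. Nor do the documents give any means of enforcing a contraception rule on someone who has left, so advice given beforehand is the working safeguard in any case. The consent form might already say six months, and then little practical gap would remain.

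Much of this stands. It limits the practical effect, and it means that the texts differ without making compliance impossible. It does not justify a mandatory floor below the advised one.

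A reader might also infer that three months exposes patients to harm. The documents do not support that. They show no harm at three months, give no reason for choosing six, and report a half-life of little more than an hour. Nor can a reader infer that patients are being told three months, because the consent pages are not in the text available.

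The affected group is probably small. Section 5.4.5 caps enrolment at 38, and section 10 refers to a single patient on study at Amendment G. To be affected, a patient must be fertile, leave before month six (under reading A), and rely on 2.1.13 despite the six-month advice.

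**Conclusion.** The inconsistency is real and lies in current text. The mandatory period in 2.1.13 falls short of the protocol's own advised minimum by up to three months. The shortfall applies to patients off study before month six if participation includes follow-up, or to all fertile patients if it means treatment only. The first reading is better supported, so a flat statement that every fertile patient is three months short would go too far.

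The conclusion rests on two assumptions: that both periods run from the last dose, and that no unseen text reconciles them. The number of patients affected and any added risk between months three and six cannot be estimated from the documents. There is no effect on sample size, error rates or analysis. This is a minor safety-text correction: the mismatch in wording is certain, and its practical effect is small or unknown.

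**What to change.** In 2.1.13, replace *three months* with *at least six months* and leave the rest of the sentence as it is. Then check that the consent form and any other patient-facing text give the same period.

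The edit should go no further. A rewrite that limited the duty to fertile patients and ended it six months after the last dose would drop both the coverage of all patients and the clause on participation. Under reading A, that would shorten the obligation for anyone followed beyond month six.

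The cost is a change of period in one sentence, a check of patient-facing text, and up to three more months of required contraception. The extra time is less where participation already ran past month three. No new tests or patients are needed.

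If the sponsor prefers three months, the alternative is to justify it and change the Cautions to match. The protocol offers no such justification now, so aligning to six is the conservative choice.
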